# **12 APPENDICES**

ACT-539313 Binge Eating Disorder Protocol ID-082A201 Final Version 3 4 May 2021, page 108/140

Confidential

Doc No D-21.148
ACT-539313 Binge Eating Disorder Protocol ID-082A201 Final Version 3 4 May 2021, page 109/140

ACT-539313 Binge Eating Disorder Protocol ID-082A201 Final Version 3 4 May 2021, page 110/140

ACT-539313 Binge Eating Disorder Protocol ID-082A201 Final Version 3 4 May 2021, page 111/140

ACT-539313 Binge Eating Disorder Protocol ID-082A201 Final Version 3 4 May 2021, page 112/140

ACT-539313 Binge Eating Disorder Protocol ID-082A201 Final Version 3 4 May 2021, page 113/140

ACT-539313 Binge Eating Disorder Protocol ID-082A201 Final Version 3 4 May 2021, page 114/140

ACT-539313 Binge Eating Disorder Protocol ID-082A201 Final Version 3 4 May 2021, page 115/140

ACT-539313 Binge Eating Disorder Protocol ID-082A201 Final Version 3 4 May 2021, page 116/140

ACT-539313 Binge Eating Disorder Protocol ID-082A201 Final Version 3 4 May 2021, page 117/140

ACT-539313 Binge Eating Disorder Protocol ID-082A201 Final Version 3 4 May 2021, page 118/140

ACT-539313 Binge Eating Disorder Protocol ID-082A201 Final Version 3 4 May 2021, page 119/140

ACT-539313 Binge Eating Disorder Protocol ID-082A201 Final Version 3 4 May 2021, page 120/140

ACT-539313 Binge Eating Disorder Protocol ID-082A201 Final Version 3 4 May 2021, page 121/140

ACT-539313 Binge Eating Disorder Protocol ID-082A201 Final Version 3 4 May 2021, page 122/140

ACT-539313 Binge Eating Disorder Protocol ID-082A201 Final Version 3 4 May 2021, page 123/140

Confidential

- Ing 2021, page 123/140

ACT-539313 Binge Eating Disorder Protocol ID-082A201 Final Version 3 4 May 2021, page 124/140

ACT-539313 Binge Eating Disorder Protocol ID-082A201 Final Version 3 4 May 2021, page 125/140

ACT-539313 Binge Eating Disorder Protocol ID-082A201 Final Version 3 4 May 2021, page 126/140

ACT-539313 Binge Eating Disorder Protocol ID-082A201 Final Version 3 4 May 2021, page 127/140

ACT-539313 Binge Eating Disorder Protocol ID-082A201 Final Version 3 4 May 2021, page 128/140

ACT-539313 Binge Eating Disorder Protocol ID-082A201 Final Version 3 4 May 2021, page 129/140

ACT-539313 Binge Eating Disorder Protocol ID-082A201 Final Version 3 4 May 2021, page 130/140

ACT-539313 Binge Eating Disorder Protocol ID-082A201 Final Version 3 4 May 2021, page 131/140

ACT-539313 Binge Eating Disorder Protocol ID-082A201 Final Version 3 4 May 2021, page 132/140

ACT-539313 Binge Eating Disorder Protocol ID-082A201 Final Version 3 4 May 2021, page 133/140

ACT-539313 Binge Eating Disorder Protocol ID-082A201 Final Version 3 4 May 2021, page 134/140

ACT-539313 Binge Eating Disorder Protocol ID-082A201 Final Version 3 4 May 2021, page 135/140

ACT-539313 Binge Eating Disorder Protocol ID-082A201 Final Version 3 4 May 2021, page 136/140

ACT-539313 Binge Eating Disorder Protocol ID-082A201 Final Version 3 4 May 2021, page 137/140

ACT-539313 Binge Eating Disorder Protocol ID-082A201 Final Version 3 4 May 2021, page 138/140

ACT-539313 Binge Eating Disorder Protocol ID-082A201 Final Version 3 4 May 2021, page 139/140

ACT-539313 Binge Eating Disorder Protocol ID-082A201 Final Version 3 4 May 2021, page 140/140

ndorsia

ACT-539313

STATISTICAL ANALYSIS PLAN

FOR CLINICAL STUDY REPORT

ID-082A201

Version 3

Multicenter, double-blind, randomized, placebo-controlled, parallel-group, proof-of-concept study to evaluate the efficacy and safety of oral ACT-539313 in the treatment of adults with moderate to severe binge eating disorder

Document Number: D-22.100

1 April 2022

Property of Idorsia Pharmaceuticals Ltd

Confidential

May not be used, divulged, published or otherwise disclosed without the consent of Idorsia Pharmaceuticals Ltd

Revision history

Version date	Version	Implemented change(s)	
23 September 2021	1	Initial version	
9 February 2022	2	 Section 4.1: Added reason for exclusion from FAS. Section 4.1.4: Updated compliance threshold for exclusion from PPS. Section 5.3.1: Updated demographic summary for screen failures. Section 5.3.4: Removed summary for study participants currently receiving psychological or behavioral weight-loss interventions for BED. Section 5.4.2: Updated the calculation of treatment compliance and the treatment interruption definition. Section 6.1.3: Added use of sandwich estimator, model diagnostic for normality assumption, and non-parametric method in case normality assumption is not met. Section 6.1.6: Added one sensitivity analysis so called delta-adjusted tipping point. Section 7.3: Removed summary table for change from baseline to last value in the treatment period for hematology and blood chemistry parameters. Updated list of laboratory parameters considered for the shift table. Added boxplots for main laboratory parameters. Section 7.6: Updated summary and graphic presentation of SSS score. Section 11.2; Updated Table 6 and added a sentence for the time window to be considered for the SSS calculation. Section 14.1: Updated the SAS code to account for model diagnostic and sandwich estimator. 	

Doc No D-22,100	ACT-539313 ID-082A201 1 April 2022, page 3/60	Confidential	Statistical Analysis Plan for Clinical Study Report Version 3
			Doc No D-22.100

PD	Protocol deviation
PGI-C	Patient Global Impression of Change scale
PGI-S	Patient Global Impression of Severity scale
РК	Pharmacokinetic
POC	Proof-of-concept
PPS	Per-protocol set
PT	Preferred term
QTc	Corrected QT interval
QTcB	QT interval corrected according to Bazett's formula
QTcF	QT interval corrected according to Fridericia's formula
RND	All-randomized analysis set
SAE	Serious adverse event
SAF	Safety analysis set
SAP	Statistical analysis plan
SCR	Screened analysis set
SD	Standard deviation
SE	Standard error
SI	International system of units

ACT-539313 ID-082A201 1 April 2022, page 10/60	ConfidentialStatistical Analysis Plan for Clinical Study Report Version 3 Doc No D-22.100
SOC	System organ class
SSS	Stanford Sleepiness Scale
Т3	Tri-iodothyronine
T4	Thyroxine
TEAE	Treatment-emergent adverse event
TSH	Thyroid stimulating hormone
ULN	Upper limit of normal
USA	United States of America
WHO	World Health Organization
YBOCS-BE	Yale-Brown Obsessive-Compulsive Scale modified for Binge Eating

ACT-539313		Statistical Analysis Plan
ID-082A201	-082A201 Confidential	for Clinical Study Report
1 April 2022, page 11/60	Conndential	Version 3
		Doc No D-22.100

1 INTRODUCTION

This SAP describes in detail the analyses and data presentation for the CSR prepared for ID-082A201.

Obvious corrections to address minor formatting errors or spelling mistakes may be performed at the time of analysis without amending this and related documentation (e.g., mock shells).

Data will be analyzed by Idorsia and/or designated CROs supervised by Idorsia using SAS[®] version 9.4 or higher and R version 3.4.3 or higher.

This SAP is based on Version 3 of Protocol ID-082A201, dated 4 May 2021 [Table 1].

Table 1Study documents

Document	Date, Version	
Clinical Study Protocol (CSP)	04MAY2021, Version 3	
eCRF specifications	01FEB2021, Version 2	
Protocol deviation list	21JAN2022, Version 4	

During the drafting of the current SAP, three sites withdrew from the study due to financial reasons related to COVID-19: sites 1012, 1015, and 1061. Consequently, all study participants randomized in these sites discontinued treatment and finished the study. Section 6 describes how these study participants will be considered for the efficacy analyses.

2 STUDY DESIGN AND FLOW

[figure not shown]
This is a Phase 2, multicenter, double-blind, randomized, placebo-controlled, parallel-group, proof-of-concept study assessing ACT-539313 at a dosing regimen of 100 mg b.i.d. vs placebo over a 12-week treatment period in adult participants (18 to 55 years of age) with moderate to severe binge eating disorder (BED).

Approximately 120 participants will be randomized to either ACT-539313 at a dose of 100 mg b.i.d., or placebo in a 1:1 ratio.

The study will be conducted at approximately 30 sites in the USA.

The study design is shown in Figure 1.

Figure 1Study design for ID-082A201

b.i.d. = twice daily; EOS = End-of-Study; EOT = End-of-Treatment; V = Visit.

The study comprises the following 3 periods: the screening period, the treatment period and the safety follow-up period.

The **screening period** starts with the signing of the ICF at Visit 1 and ends with Randomization at Visit 2 or with a screening failure. It lasts a minimum of 14 days and up to 28 days.

The **treatment period** starts with the administration of the first dose of study treatment and ends on the day of the last dose of study treatment. The study participants will be treated for 12 weeks.

The **safety follow-up period** starts on the day after the last dose of study treatment and ends at the EOS visit (10 ± 3 days after EOT).

See Section 11.2 for detailed definitions of the study periods.

3 OBJECTIVES

The overall objective of this POC study is to evaluate the clinical efficacy, safety and tolerability of ACT-539313 100 mg administered b.i.d. compared to placebo in adult participants with moderate to severe BED over a period of 12 weeks.

3.1 Primary objectives

To assess the efficacy of 100 mg ACT-539313 in the treatment of BED.

3.2 Secondary objectives

Not applicable.

3.3 Safety objectives

To assess the safety of ACT-539313 in participants with BED.

4 ANALYSIS SETS

4.1 Definitions of analysis sets

A study participant must have given informed consent before being included in any analysis set.

The number of study participants in each analysis set defined below will be tabulated. Any study participant excluded along with reason(s) for exclusion from the FAS, PPS, or PK analysis sets will be summarized and listed.

4.1.1 Screened set

The Screened set (SCR) includes all study participants who entered screening and have a subject number.

Summaries based on the SCR set will be presented as one group (i.e., all study participants) unless otherwise specified.

4.1.2 All randomized set

The All-randomized analysis set (RND) includes all study participants from the SCR who were randomized.

4.1.3 Full analysis set

The Full analysis set (FAS) includes all study participants who were randomized, received at least one dose of study treatment, and have a baseline assessment of the primary endpoint.

In order to adhere to the intention-to-treat principle as much as possible, study participants will be evaluated according to the treatment they have been assigned to, which may differ from the treatment they received.

4.1.4 Per-protocol set

The Per-protocol set (PPS) includes all study participants from the FAS who complied with the protocol sufficiently to be likely to exhibit the treatment effects.

Criteria for sufficient compliance:

- Absence of important PDs, which may affect the primary endpoint, leading to exclusion from the PPS, as defined in a separate PD document that will be finalized before unblinding.
- Study treatment compliance is $\geq 80\%$ [as calculated in Section 5.4.2].
- Absence of premature treatment discontinuation.

ACT-539313		Statistical Analysis Plan
ID-082A201	Confidential	for Clinical Study Report
1 April 2022, page 14/60	Confidential	Version 3
		Doc No D-22.100

Study participants not meeting the criteria for sufficient compliance will be excluded from the PPS. Study participants will be evaluated according to the treatment they have been assigned to.

4.1.5 Safety set

The Safety set (SAF) includes all randomized study participants who received at least one dose of study treatment.

Study participants will be evaluated according to the actual treatment they received, which may differ from the randomly assigned treatment.

Actual treatment received is defined as the assigned study treatment when received at least once, or the other study treatment if the assigned study treatment was never received.

4.1.6 Pharmacokinetic analysis set

The Pharmacokinetic (PK) analysis set includes all study participants in the SAF who have at least one PK sample collected after initiation of study treatment.

Study participants will be evaluated according to the actual treatment they received. Study participants receiving placebo will be excluded from the PK set.

4.2 Usage of the analysis sets

The analyses of efficacy endpoints will be performed using the FAS, and the PPS for supportive analysis.

The RND will be used for the analysis of demographic and baseline disease characteristics, and the SCR set to provide the same summaries for the screen failures.

The SAF will be used for the analysis of safety endpoints (including previous and concomitant medication, and study treatment exposure).

The PK set will be used for the analysis of ACT-539313 plasma concentrations.

Study participants' listings will be based on the SAF, unless otherwise specified. Subject disposition will be described for the SCR.

ACT-539313		Statistical Analysis Plan
ID-082A201 Confidential	for Clinical Study Report	
1 April 2022, page 15/60	Conndential	Version 3
		Doc No D-22.100

Table 2Usage of analysis datasets

Analysis	SCR	RND	FAS	PPS	SAF	PK set
Subject disposition	Х					
Demographics and baseline disease characteristics	х	Х				
Previous and concomitant medication					Х	
Study drug exposure					Х	
Efficacy analysis			Х	(x)		
Safety and tolerability analyses					Х	
PK data analysis						Х

Note: X: main analysis, (x): only if > 10% difference in size with FAS.

FAS = Full analysis set; PK = pharmacokinetic; PPS = Per-protocol analysis set; RND = Randomized analysis set; SAF = Safety analysis set; SCR = Screened analysis set.

5 SUBJECT VARIABLES AND ANALYSES

5.1 Subject disposition

5.1.1 Screening failures

Screening failures will be summarized based on the SCR set and will include:

- Number (%) of study participants who did not successfully complete the screening period (based on 'Was the subject randomized?' recorded as 'No' in the 'Randomization' page).
- Primary reason for screen failure (based on reason for not randomized entered on the 'Randomization' page).

The eligibility criteria not met will be summarized. All reasons for screening failure will be listed.

Of note: No re-screening is allowed in the study.

5.1.2 Study disposition

Study participant disposition will be summarized based on the SCR, presented by randomized treatment group and all screened study participants combined, and will include:

- Number of study participants screened.
- Number (%) of study participants randomized (based on non-missing randomization number).
- Number (%) of study participants who received study treatment during the treatment period (based on non-missing 'Treatment start date' in the 'Study Treatment Log' page). Percentage will be based on randomized subjects.

ACT-539313		Statistical Analysis Plan
ID-082A201	Confidential	for Clinical Study Report
1 April 2022, page 16/60	Confidential	Version 3
		Doc No D-22,100

- Number (%) of study participants who completed the treatment period (based on 'Reason for treatment stop' entered as 'Completion as per protocol' in the 'Study Treatment Log' page). Percentage will be based on study participants who received study treatment.
- Number (%) of study participants completing the study (based on 'Did the subject complete the study?' recorded as 'Yes' in the 'End of Study Status' page). Percentage will be based on randomized subjects.

5.1.3 Study and study treatment completion/discontinuation

The following summary will be based on the SAF and presented by treatment group and all treatment groups combined:

- Number (%) of study participants who prematurely discontinued study treatment (based on 'Reason for treatment stop' entered as 'Discontinuation' in the 'Study Treatment Log' page).
- Primary reason for premature study treatment discontinuation (based on 'Discontinuation, Reason' entered on the 'Study Treatment Log' page).

The following summary will be based on the RND and presented by treatment group and all treatment groups combined:

- Number (%) of study participants who prematurely discontinued from the study (based on non-missing reason for stopping study entered in the 'End of Study Status' page).
- Primary reason for premature discontinuation from the study (based on 'Study stopped due to' entered in the 'End of Study Status' page).

All reasons for premature study treatment discontinuation and study discontinuation will be listed based on the RND.

5.1.4 Study enrollment

The number (%) of screened study participants as well as randomized will be displayed by site based on the SCR by treatment group and all treatment groups combined.

The randomization scheme and codes will be listed for randomized study participants only.

5.2 **Protocol deviations**

The RND will be used for the summary of PDs. All PDs and important PDs will be summarized in separate tables as per pre-specified category (i.e., selection criteria, Investigational Medicinal Product, study conduct/procedure, forbidden medication, withdrawal criteria and other) by treatment group and all treatment groups combined. In addition, the same summary of all PDs and important PDs will be provided separately for PDs related to COVID-19.

ACT-539313		Statistical Analysis Plan
ID-082A201	Confidential	for Clinical Study Report
1 April 2022, page 17/60	Confidential	Version 3
		Doc No D-22.100

A study participant with multiple occurrences of a protocol deviation is counted only once per protocol deviation category.

A listing of protocol deviations will be provided using the SCR. PDs related to COVID-19 will be flagged in the listings.

5.3 Subject characteristics

Unless noted otherwise, summaries and listings described in this section will be based on the RND.

Summaries will be provided for all treatment groups combined as well as by treatment group separately. Data will be listed individually by study participant.

5.3.1 Demographics

Demographic data at screening, including age, sex, race, ethnicity, height, weight and BMI will be summarized and listed.

The number (%) of study participants randomized in each age category (< 30, \geq 30 years at screening), and in each BMI category (< 30, \geq 30 kg/m² at screening), will be further summarized.

The same summary and listing will be provided also for screen failures. Height, weight and BMI will not be shown since these variables are not collected for screen failures.

5.3.2 Baseline disease characteristics

Baseline disease characteristics include BE severity based on number of BE days per week and on number of BE episodes per week (both assessed during the two weeks prior to randomization [see Section 11.4 for baseline definition]). In addition, CGI-S, PGI-S, YBOCS-BE total score, HAMD-17 total score and EDE-Q total score assessed at randomization will be described.

These baseline disease characteristics will be listed and summarized.

5.3.3 Medical history and concomitant diseases at screening

Relevant medical history and current medical conditions will be coded using MedDRA.

Any disease or diagnosis is defined as previous if 'Ongoing at informed consent' is answered as 'No'; all other diseases/diagnoses are considered as study concomitant (where answer is 'Yes').

Medical history and current (ongoing) medical conditions, excluding BED and BEDrelated symptoms, will be summarized separately, and listed. Summaries will be presented for each treatment group by primary SOC and PT. Medical history will be sorted by SOC and PT within each SOC by descending frequency based on all treatment groups combined.

ACT-539313		Statistical Analysis Plan
ID-082A201	Confidential	for Clinical Study Report
1 April 2022, page 18/60	Confidential	Version 3
		Doc No D-22 100

The MedDRA version used for reporting will be specified in the footnote of the applicable output.

5.3.4 **Previous and concomitant therapy**

Previous and concomitant therapies will be coded using the WHO Drug Global reference dictionary that employs the WHO ATC classification system. The WHO Drug Global version used for reporting will be specified in the footnote of the applicable output.

Previous therapies are any treatments for which the end date is prior to signing of the ICF. Any previous therapy is to be recorded in the 'Previous/Concomitant Medication' page if discontinued less than 30 days prior to signing of the informed consent form.

Study-concomitant therapies are any treatments that are either ongoing at the signing of informed consent or initiated during the time from the signing of informed consent up to EOS. The use of all study-concomitant therapies (including contraceptives and traditional and alternative medicines, e.g., plant-, animal-, or mineral-based medicines) is to be recorded in the 'Previous/Concomitant Medication' page.

Study treatment-concomitant therapies (a subset of study-concomitant therapies) are any treatments that are either ongoing at the start of study treatment or initiated during the study period until 1 day after the last dose of study treatment.

The number (%) of study participants having taken at least one previous or concomitant therapy will be summarized by ATC classification level 4 (or next highest available level) and individual preferred name within each ATC classification based on the SAF. Previous and concomitant therapy will be sorted by ATC class and preferred name within each ATC class by descending frequency based on all treatment groups combined.

Summary tables will be provided for previous, study-concomitant and study treatment-concomitant therapies separately. All concomitant therapies will be listed using the SAF and those related to an AE will be flagged.

5.4 Study treatment exposure and compliance

Summaries and listings described in this section will be based on the SAF.

5.4.1 Exposure

The duration of study treatment (including categories: $\leq 1, \geq 1-2, \geq 2-4, \geq 4-6, \geq 6-8, \geq 8-10, \geq 10-12, \geq 12-13, \geq 13$ weeks) will be summarized.

The duration of treatment (in days) is defined as the difference between the treatment end date and the treatment start date plus one day. This calculation ignores periods of treatment interruption.

ACT-539313		Statistical Analysis Plan
ID-082A201	Confidential	for Clinical Study Report
1 April 2022, page 19/60	Confidential	Version 3
		Doc No D-22.100

In addition, time from first dose of study treatment to treatment discontinuation will be summarized by treatment group using Kaplan-Meier plots.

The duration of treatment along with reason for treatment stop will be listed.

5.4.2 Compliance with study treatment

Study treatment compliance will be assessed through study treatment dispensing and accountability.

The following formula will be used to calculate compliance for the treatment period:

Study treatment compliance (%) = [(number of capsules dispensed – number of capsules returned^{*}) / (treatment duration – total duration of treatment interruptions)] $\times 0.5^{**} \times 100$

* If a study participant did not return his/her bottle (e.g., it is lost), compliance will not be calculated, and the compliance will be set to missing.

** To account for 2 capsules taken per day (i.e., b.i.d.).

Treatment duration and total duration of treatment interruptions are calculated using the dedicated eCRF page 'Study Treatment Log' as follows:

- Treatment duration (days) = date of last drug intake of study treatment date of first drug intake of study treatment + 1 day.
- Total duration of treatment interruptions (days) is the sum of all the treatment interruptions' durations. A treatment interruption duration = date restarted study treatment end date of study treatment due to an interruption. For example, if a study participant stopped his/her treatment on 19MAR2021 and started again on 23MAR2021, as the treatment is taken on the start and end dates, the calculation will be 23MAR2021 19MAR2021 = 4 days of interruption. Should the study participant interrupt the treatment again for 7 days, the total duration of interruptions will be 11 days. Moreover, if a study participant misses one dose, either the evening or the morning dose, a treatment interruption of 1 day will be counted.

Study treatment compliance (including categories 0%, > 0% – < 50%, 50% – < 70%, 70% – < 80%, 80% – < 90%, 90% – < 100%, 100%, > 100%), treatment interruptions (Yes/No), and duration of treatment interruptions will be summarized.

The number (%) of study participants who have treatment interruptions, and the corresponding reasons will be tabulated.

Study treatment compliance, dispensing and accountability data will be listed.

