#### 5.9.1 Study treatment premature discontinuation

The decision to prematurely discontinue study treatment may be made by the study participant, the investigator/delegate, or the sponsor personnel.

The investigator/delegate has the option of prematurely discontinuing study treatment for a given study participant in response to an AE, a diagnostic or therapeutic procedure, a laboratory abnormality, or for administrative reasons. If study treatment is interrupted by the study participant for any reason, she/he must inform the investigator/delegate as soon as possible. Study treatment dose interruptions must be recorded in the eCRF.

The investigator/delegate must permanently discontinue study treatment for a given study participant if, on balance, he/she believes that continued administration would be contrary to the best interests of the study participant.

Study-specific criteria for permanent discontinuation of study treatment are described in Sections 5.9.1.1 to 5.9.1.4.

The main reason for permanent discontinuation of study treatment (e.g., due to pre-specified study treatment discontinuation criteria, an AE, lack of efficacy, study termination) must be documented in the eCRF.

A study participant who prematurely discontinues study treatment is not considered as withdrawn from the study.

The study participant who prematurely discontinues study treatment or who is permanently discontinued from study treatment will be asked to return for an EOT visit within 1 to 5 days of last intake of study treatment and thereafter to attend follow-up visits as defined in the schedule of activities [Table 1, Section 7.2].

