6.1.7 Supportive analyses

The main analysis performed for the primary efficacy endpoint [Section 6.1.3] will be repeated using the PPS to assess the effect protocol deviations may have on the results.

In addition, the main analysis performed for the primary efficacy endpoint [Section 6.1.3] will be repeated considering all data collected to evaluate the effect intercurrent events may have on the results (see Section 14.12 for the list of BE forbidden medications).

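### The compliance formula raises the value for a logged missed dose, so the 80% per-protocol criterion does not respond to logged non-adherence

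*SAP*

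**What the plan says.** SAP 5.4.2 defines compliance as capsules dispensed minus capsules returned, divided by "treatment duration – total duration of treatment interruptions", times 0.5 for two capsules a day, times 100. Interruption lengths come from the Study Treatment Log page of the eCRF and are restart date minus stop date. The worked example has a 4-day interruption and then another: "Should the study participant interrupt the treatment again for 7 days, the total duration of interruptions will be 11 days". The section ends with the rule that "if a study participant misses one dose, either the evening or the morning dose, a treatment interruption of 1 day will be counted".

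SAP 4.1.4 makes this value one of three conditions for the PPS: "Study treatment compliance is $\geq 80\%$ [as calculated in Section 5.4.2"]. There is no upper limit. The other two conditions are absence of important protocol deviations (listed in a separate document that is not supplied) and absence of premature treatment discontinuation. The stated purpose of the set is to hold participants "who complied with the protocol sufficiently to be likely to exhibit the treatment effects". SAP 6.1.7 has the main analysis "repeated using the PPS to assess the effect protocol deviations may have on the results".

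On data entry, protocol 5.9.1 says: "Study treatment dose interruptions must be recorded in the eCRF". It does not say that a single missed dose is an interruption; only the SAP does.

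**The concern.** The formula treats a logged lapse as time when no drug was due. For a single missed dose it goes further: one capsule was missed, but a whole day, worth two capsules, leaves the expected count. A measure of adherence should fall when a dose is missed, and this one rises. Misses found only through the capsule count still lower it. Two participants with the same intake can therefore get different values, and the one with the better-kept log gets the higher value. Logged misses can also hide unlogged ones.

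At stake is whether the 80% criterion can pick out low exposure, which is what SAP 4.1.4 wants from the PPS and what SAP 6.1.7 relies on. The compliance table is affected too, because its category above 100% would mix people who missed doses with people who took too many.

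**Working it through.** **The SAP's own figure.** 23 March minus 19 March is 4 days, and 4 + 7 = 11 days. This reproduces.

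**Inputs.** Twelve weeks at two capsules a day is 168 capsules due. If the first dose is taken in the evening and the last in the morning, as protocol 6.1.6.3 suggests, these span D = 85 dates: 1 on Day 1, 166 on Days 2 to 84, and 1 on Day 85. D = 84 is given in brackets throughout. True adherence is capsules taken divided by 168.

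**Direction for a single miss.** With N capsules taken over D days, one logged miss changes N/D to (N − 1)/(D − 1). The new ratio is larger whenever N > D, that is, whenever compliance exceeds 50%.

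**k logged single misses.** SAP value = (168 − k)/(D − k) × 50.

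| k | SAP value, D = 85 | [D = 84] | True |
|---|---|---|---|
| 0 | 168/85 × 50 = 98.8% | [100.0%] | 100.0% |
| 10 | 158/75 × 50 = 105.3% | [106.8%] | 94.0% |
| 20 | 148/65 × 50 = 113.8% | [115.6%] | 88.1% |
| 34 | 134/51 × 50 = 131.4% | [134.0%] | 79.8% |

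The same 34 misses with none logged give 134/85 × 50 = 78.8% [79.8%], a fail. Logging just two of the 34 [one] gives 134/83 × 50 = 80.7%, a pass.

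**Multi-day gaps.** A restart L days after the stop date, with drug taken on both dates, misses 2L − 2 to 2L capsules and removes L days.

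- SAP example (L = 4 and L = 7): 18 to 22 capsules missed and 11 days removed. The range is 150/74 × 50 = 101.4% down to 146/74 × 50 = 98.6% [102.7% to 100.0%]. True adherence is 150/168 = 89.3% down to 146/168 = 86.9%.
- One 18-day gap: 34 to 36 capsules missed. The range is 134/67 × 50 = 100.0% down to 132/67 × 50 = 98.5% [101.5% to 100.0%]. True adherence is 79.8% down to 78.6%.

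**Masking.** With k logged single misses and u unlogged, find the first u for which (168 − k − u)/(D − k) × 50 is below 80.

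| k logged | Total misses to fail, D = 85 | True | [D = 84] | [True] |
|---|---|---|---|---|
| 0 | 33 (135/85 × 50 = 79.4%) | 80.4% | [34] | [79.8%] |
| 10 | 49 (119/75 × 50 = 79.3%) | 70.8% | [50] | [70.2%] |
| 20 | 65 (103/65 × 50 = 79.2%) | 61.3% | [66] | [60.7%] |

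**The case against.** Several points can be made for the plan.

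- **Intent.** Leaving interruptions out of the denominator gives adherence while on treatment, a recognised measure. The SAP revision history shows that the calculation was changed on purpose in version 2 and clarified in version 3. The one-day rule is whole-day rounding from a log that holds dates. This can explain leaving out multi-day gaps. It does not explain values above 100% in someone who missed doses, and on-treatment adherence is not what SAP 4.1.4 says the PPS is meant to capture.
- **Gaps do not always raise the value.** On 85 dates, a fully missed 11-day total moves it from 98.8% to 98.6%. For someone already below 100% a gap can lower it slightly: on 84 dates, 143/84 × 50 = 85.1% becomes 135/80 × 50 = 84.4% after an 8-capsule, 4-day gap. This stands. The rise is a result for single misses; for gaps the point is insensitivity.
- **Logging frequency is unknown.** The eCRF specifications are not supplied, and 20 or 34 separately logged single misses may be rare. This stands as a limit on the largest figures, but not on the gap result, since the protocol requires interruptions to be recorded.
- **No changed decision is shown.** The SAP's example participant passes 80% either way. The unseen deviation list may exclude long interruptions, and discontinuation excludes independently. This stands.
- **Other safeguards.** SAP 5.4.2 tabulates interruptions and their reasons, and protocol 8.1.7 has overdoses recorded as adverse events. These help a reader of the tables but do not enter the 80% criterion.
- **Cost of the remedy.** Without the deduction, holds that follow protocol procedure also lower the value, such as dispensing withheld after certain C-SSRS answers (protocol 7.2.5.7). This is a real but small cost, and it fits a set defined by likely exposure to a treatment effect.

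**Conclusion.** The concern holds. Each logged single miss raises compliance whenever the value is above 50%, and a logged gap of any length leaves an otherwise adherent participant near 100%. On 84 dates, if every miss is logged, the value cannot fall below 100%, so the criterion cannot be failed. For logged non-adherence the 80% criterion does not do its stated job.

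The reach is limited. The FAS primary analysis does not use this value. The effect is on the compliance summary, one of three PPS criteria, and the supportive analysis on that set. A changed result on the criterion needs about 33 or more missed doses of 168, and the documents do not say how many participants reach that. Table 2 of SAP 4.2 makes the PPS efficacy analysis depend on a size difference of more than 10% from the FAS; a change in whether that is met is possible but not shown.

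The figures assume 168 capsules due over 84 or 85 dates, with gaps counted as in the SAP example. The conclusion is the same for both day counts. The correction should be made, but it is not critical to the trial's main result.

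**What to change.** Before unblinding:

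1. For the 80% criterion, compute (dispensed − returned)/(2 × treatment duration in days) × 100, with no interruptions subtracted, and state in SAP 4.1.4 that the 80% refers to the full treatment duration. The SAP example participant would then read 150/85 × 50 = 88.2% down to 146/85 × 50 = 85.9% [89.3% to 86.9%], close to true adherence.
2. If adherence while on treatment is wanted, report it as a separate descriptive line that is not used for the PPS.
3. Keep the planned interruption summary. Count a single miss there as half a day only if the Study Treatment Log identifies individual doses, because dates alone cannot separate one missed dose from two consecutive ones. Switching to half a day while still subtracting it would not be enough: on 84 dates, (168 − k)/(84 − k/2) × 50 equals 100% for every k.

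The cost is SAP wording and one derivation, with no new data. Compliance figures will fall and the PPS may shrink slightly. On 85 dates a fully adherent participant reads 98.8%, and 33 misses (true 80.4%) read 79.4%. Both already happen under the current formula when nothing is logged.
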